8.3. Special Situations

8.3.1. Protocol-Specified Serious Adverse Events

There are no protocol-specified SAEs in this study. All SAEs will be reported to Pfizer Safety by the investigator as described in previous sections, and will be handled as SAEs in the safety database.

8.3.2. Potential Cases of Drug-Induced Liver Injury

Humans exposed to a drug who show no sign of liver injury (as determined by elevations in transaminases) are termed “tolerators,” while those who show transient liver injury, but adapt

are termed “adaptors.” In some subjects, transaminase elevations are a harbinger of a more serious potential outcome. These subjects fail to adapt and therefore are “susceptible” to progressive and serious liver injury, commonly referred to as drug-induced liver injury (DILI). Subjects who experience a transaminase elevation above 3 times the upper limit of normal (\times ULN) should be monitored more frequently to determine if they are an “adaptor” or are “susceptible.”

In the majority of DILI cases, elevations in aspartate aminotransferase (AST) and/or alanine aminotransferase (ALT) precede total bilirubin (TBili) elevations ($>2 \times$ ULN) by several days or weeks. The increase in TBili typically occurs while AST/ALT is/are still elevated above $3 \times$ ULN (ie, AST/ALT and TBili values will be elevated within the same lab sample). In rare instances, by the time TBili elevations are detected, AST/ALT values might have decreased. This occurrence is still regarded as a potential DILI. Therefore, abnormal elevations in either AST OR ALT in addition to TBili that meet the criteria outlined below are considered potential DILI (assessed per Hy’s law criteria) cases and should always be considered important medical events, even before all other possible causes of liver injury have been excluded.

The threshold of laboratory abnormalities for a potential DILI case depends on the subject’s individual baseline values and underlying conditions. Subjects who present with the following laboratory abnormalities should be evaluated further as potential DILI (Hy’s law) cases to definitively determine the etiology of the abnormal laboratory values:

- Subjects with AST/ALT and TBili baseline values within the normal range who subsequently present with AST OR ALT values $>3 \times$ ULN AND a TBili value $>2 \times$ ULN with no evidence of hemolysis and an alkaline phosphatase value $<2 \times$ ULN or not available;
- For subjects with baseline AST **OR** ALT **OR** TBili values above the ULN, the following threshold values are used in the definition mentioned above, as needed, depending on which values are above the ULN at baseline:
 - Preexisting AST or ALT baseline values above the normal range: AST or ALT values >2 times the baseline values AND $>3 \times$ ULN; or $>8 \times$ ULN (whichever is smaller).
 - Preexisting values of TBili above the normal range: TBili level increased from baseline value by an amount of at least $1 \times$ ULN **or** if the value reaches $>3 \times$ ULN (whichever is smaller).

Rises in AST/ALT and TBili separated by more than a few weeks should be assessed individually based on clinical judgment; any case where uncertainty remains as to whether it represents a potential Hy’s law case should be reviewed with the sponsor.

The subject should return to the investigator site and be evaluated as soon as possible, preferably within 48 hours from awareness of the abnormal results. This evaluation should include laboratory tests, detailed history, and physical assessment.

In addition to repeating measurements of AST and ALT and TBili, laboratory tests should include albumin, creatine kinase (CK), direct and indirect bilirubin, gamma-glutamyl transferase (GGT), prothrombin time (PT)/international normalized ratio (INR), total bile acids, alkaline phosphatase and acetaminophen drug and/or protein adduct levels. Consideration should also be given to drawing a separate tube of clotted blood and an anticoagulated tube of blood for further testing, as needed, for further contemporaneous analyses at the time of the recognized initial abnormalities to determine etiology. A detailed history, including relevant information, such as review of ethanol, acetaminophen (either by itself or as a coformulated product in prescription or over-the-counter medications), recreational drug, supplement (herbal) use and consumption, family history, sexual history, travel history, history of contact with a jaundiced person, surgery, blood transfusion, history of liver or allergic disease, and potential occupational exposure to chemicals, should be collected. Further testing for acute hepatitis A, B, C, D, and E infection and liver imaging (eg, biliary tract) may be warranted.

All cases demonstrated on repeat testing as meeting the laboratory criteria of AST/ALT and TBili elevation defined above should be considered potential DILI (Hy's law) cases if no other reason for the LFT abnormalities has yet been found. **Such potential DILI (Hy's law) cases are to be reported as SAEs, irrespective of availability of all the results of the investigations performed to determine etiology of the LFT abnormalities.**

A potential DILI (Hy's law) case becomes a confirmed case only after all results of reasonable investigations have been received and have excluded an alternative etiology.

8.3.3. Exposure to the Investigational Product During Pregnancy or Breastfeeding, and Occupational Exposure

Exposure to the investigational product under study during pregnancy or breastfeeding and occupational exposure are reportable to Pfizer Safety within 24 hours of investigator awareness.

8.3.3.1. Exposure During Pregnancy

For both unapproved/unlicensed products and for marketed products, an exposure during pregnancy (EDP) occurs if:

- A female becomes, or is found to be, pregnant either while receiving or having been exposed (eg, because of treatment or environmental exposure) to the investigational product; or the female becomes or is found to be pregnant after discontinuing and/or being exposed to the investigational product;
- An example of environmental exposure would be a case involving direct contact with a Pfizer product in a pregnant woman (eg, a nurse reports that she is pregnant and has been exposed to chemotherapeutic products).

- A male has been exposed (eg, because of treatment or environmental exposure) to the investigational product prior to or around the time of conception and/or is exposed during his partner's pregnancy.

If a subject or subject's partner becomes or is found to be pregnant during the subject's treatment with the investigational product, the investigator must report this information to Pfizer Safety on the CT SAE Report Form and an EDP supplemental form, regardless of whether an SAE has occurred. In addition, the investigator must submit information regarding environmental exposure to a Pfizer product in a pregnant woman (eg, a subject reports that she is pregnant and has been exposed to a cytotoxic product by inhalation or spillage) to Pfizer Safety using the EDP supplemental form. This must be done irrespective of whether an AE has occurred and within 24 hours of awareness of the exposure. The information submitted should include the anticipated date of delivery (see below for information related to termination of pregnancy).

Follow-up is conducted to obtain general information on the pregnancy and its outcome for all EDP reports with an unknown outcome. The investigator will follow the pregnancy until completion (or until pregnancy termination) and notify Pfizer Safety of the outcome as a follow-up to the initial EDP supplemental form. In the case of a live birth, the structural integrity of the neonate can be assessed at the time of birth. In the event of a termination, the reason(s) for termination should be specified and, if clinically possible, the structural integrity of the terminated fetus should be assessed by gross visual inspection (unless pre-procedure test findings are conclusive for a congenital anomaly and the findings are reported).

If the outcome of the pregnancy meets the criteria for an SAE (ie, ectopic pregnancy, spontaneous abortion, intrauterine fetal demise, neonatal death, or congenital anomaly [in a live-born baby, a terminated fetus, an intrauterine fetal demise, or a neonatal death]), the investigator should follow the procedures for reporting SAEs.

Additional information about pregnancy outcomes that are reported to Pfizer Safety as SAEs follows:

- Spontaneous abortion includes miscarriage and missed abortion;
- Neonatal deaths that occur within 1 month of birth should be reported, without regard to causality, as SAEs. In addition, infant deaths after 1 month should be reported as SAEs when the investigator assesses the infant death as related or possibly related to exposure to the investigational product.

Additional information regarding the EDP may be requested by the sponsor. Further follow-up of birth outcomes will be handled on a case-by-case basis (eg, follow-up on preterm infants to identify developmental delays). In the case of paternal exposure, the investigator will provide the subject with the Pregnant Partner Release of Information Form to deliver to his partner. The investigator must document in the source documents that the

subject was given the Pregnant Partner Release of Information Form to provide to his partner.

8.3.3.2. Exposure During Breastfeeding

Scenarios of exposure during breastfeeding must be reported, irrespective of the presence of an associated SAE, to Pfizer Safety within 24 hours of the investigator's awareness, using the CT SAE Report Form. An exposure during breastfeeding report is not created when a Pfizer drug specifically approved for use in breastfeeding women (eg, vitamins) is administered in accord with authorized use. However, if the infant experiences an SAE associated with such a drug's administration, the SAE is reported together with the exposure during breastfeeding.

8.3.3.3. Occupational Exposure

An occupational exposure occurs when, during the performance of job duties, a person (whether a healthcare professional or otherwise) gets in unplanned direct contact with the product, which may or may not lead to the occurrence of an AE.

An occupational exposure is reported to Pfizer Safety within 24 hours of the investigator's awareness, using the CT SAE Report Form, regardless of whether there is an associated SAE. Since the information does not pertain to a subject enrolled in the study, the information is not recorded on an CRF; however, a copy of the completed CT SAE Report Form is maintained in the investigator site file.

8.3.4. Medication Errors

Other exposures to the investigational product under study may occur in clinical trial settings, such as medication errors.

Safety Event	Recorded on the CRF	Reported on the CT SAE Report Form to Pfizer Safety Within 24 Hours of Awareness
Medication errors	All (regardless of whether associated with an AE)	Only if associated with an SAE

8.3.4.1. Medication Errors

Medication errors may result from the administration or consumption of the investigational product by the wrong subject, or at the wrong time, or at the wrong dosage strength.

Medication errors include:

- Medication errors involving subject exposure to the investigational product;

- Potential medication errors or uses outside of what is foreseen in the protocol that do or do not involve the participating subject.

Such medication errors occurring to a study participant are to be captured on the medication error page of the CRF, which is a specific version of the AE page.

In the event of a medication dosing error, the sponsor should be notified immediately.

Whether or not the medication error is accompanied by an AE, as determined by the investigator, the medication error is recorded on the medication error page of the CRF and, if applicable, any associated AE(s), serious and non-serious, are recorded on an AE page of the CRF.

Medication errors should be reported to Pfizer Safety within 24 hours on a CT SAE Report Form **only when associated with an SAE**.

9. DATA ANALYSIS/STATISTICAL METHODS

Methodology for summary and statistical analyses of the data collected in this trial are given here and further detailed in a statistical analysis plan (SAP), which will be dated and maintained by Pfizer.

This analysis plan may modify what is outlined in the protocol; however, any major modifications of the primary endpoint definition or its analyses will also be reflected in a protocol amendment.

9.1. Sample Size Determination

The primary efficacy analysis is to compare the ASAS20 response rate at Week 16 of the tofacitinib 5 mg BID and placebo via the normal approximation for the difference in binomial proportions. Assuming a placebo response rate of 40% for ASAS20 response at Week 16, a sample size of 120 per arm will yield about 89% power to detect a difference of at least 20% between tofacitinib 5 mg BID and placebo at a two-sided significance level of 5%. In the Phase 2 proof of concept trial A3921119, ASAS20 response rates at Week 12 were 63% and 40% for tofacitinib 5 mg BID and placebo, respectively.

9.2. Efficacy Analysis

There will be a total of 2 planned analyses conducted when all applicable subjects have completed their Week 16 and Week 48 (including follow-up) visits, respectively. The investigators, subjects and sponsor study team will remain blinded to the first 16 weeks of treatment assignment through the entire duration of the trial until database release at Week 48. The first analysis (Week 16 analysis) will include all efficacy data through Week 16 and the safety data through the data cutoff date. As the primary endpoint (ASAS20), the key secondary endpoint (ASAS40) and the other Type I error controlled secondary endpoints are at Week 16, there will be no additional adjustment made for Type I error rate at the final analysis at Week 48. The efficacy analysis results through Week 16 obtained from the Week 16 analysis will be considered final and definitive. CCI

CCI

The Week 48 analysis will be conducted when all the applicable subjects have completed their Week 48 (including follow-up) visit and the database is released. All the Week 48 analysis results will be secondary in nature. The Week 48 analysis will contain results for earlier visits prior to or at Week 16 including those for the primary endpoint and the key secondary endpoint; however they will serve as a sensitivity analysis only to ensure there are no major changes to the definitive results for the primary endpoint and the key secondary endpoint obtained at the Week 16 analysis.

9.2.1. Analysis of Primary Endpoint

The ASAS20 response rate at Week 16 is the primary efficacy endpoint in this trial. The analysis of primary endpoint will be based on the full analysis set, which includes all randomized subjects who take at least 1 dose of investigational product. For the primary analysis, the normal approximation for the difference in binomial proportions adjusting for the stratification factor (ie, prior treatment history: bDMARD-naïve vs TNFi-IR) at randomization via the Cochran–Mantel–Haenszel approach will be used to estimate the treatment effect (treatment difference, standard error, 95% confidence interval) and to test (Normal Z-test) test the superiority of tofacitinib 5 mg BID to placebo and to generate confidence interval for the difference. Missing values for any reason will be handled by setting the ASAS20 value to nonresponsive. Note that this can be viewed as a composite endpoint in the sense that a response requires the subject completes a visit of interest eg, Week 16, and achieves a response per the defined ASAS20 response criteria (otherwise it is considered a nonresponse).

Sensitivity analyses will be performed to assess robustness of the primary analysis due to missing data and will be detailed in the SAP.

9.2.2. Analysis of Secondary and Other Endpoints

Methods for the analysis of secondary endpoints and other endpoints will be enumerated in the SAP. Briefly, binary variables will follow the analyses using the normal approximation to estimating binomial proportions as described for the ASAS20 and continuous endpoints will be analyzed as change from baseline as appropriate with a mixed model for repeated measures (MMRM) that include fixed effects of treatment group, visit, and treatment-group by visit interaction, stratification factor (ie, prior treatment history: bDMARD-naïve vs TNFi-IR) at randomization, and baseline value. An unstructured variance covariance matrix will be used, provided the model converges, otherwise an alternative covariance structure will be attempted. Descriptive statistics may also be calculated and displayed.

9.2.3. Control for Type I Error Rate

This protocol is designed to establish the superiority of tofacitinib 5 mg BID to placebo for the treatment of active AS based on the primary endpoint of ASAS20 at Week 16 in subjects who have had an inadequate response to previous treatments.

All statistical tests will be conducted at the 2-sided 5% (or equivalently 1-sided 2.5%) significance level for comparing tofacitinib 5 mg BID to placebo. Type I error will be controlled at 2-sided 5% or equivalently 1-sided 2.5%.

For the primary endpoint of ASAS20 at Week 16, if the 2-sided p value is $\leq 5\%$, the superiority of tofacitinib 5 mg BID to placebo will be declared for this primary endpoint and the primary objective of this study is met. Hypothesis testing will continue to the global family of select set of secondary endpoints stated below (*Global Type I Error Control (for the primary endpoint and a select set of secondary endpoints)*). For each of the endpoints within this family, superiority of tofacitinib 5 mg BID to placebo will be declared if statistical significance is achieved under the step-down testing procedure. In addition, three other families of hypotheses, ASAS family endpoints (*Type I Error Control for Endpoints in the ASAS Family*), ASAS20's earlier time points (*Type I Error Control for ASAS20 at Earlier Time Points*) and ASAS40's earlier time points (*Type I Error Control for ASAS40 at Earlier Time Points*) will also be tested. For each of the endpoints or time points of ASAS20/ASAS40, superiority of tofacitinib 5 mg BID to placebo will be declared if statistical significance is achieved under its respective step-down testing procedure.

Global Type I Error Control (for the primary endpoint and a select set of secondary endpoints): The family-wise Type I error rate will be controlled at the 2-sided 5% (or equivalently 1-sided 2.5%) significance level using a step-down testing procedure for the primary endpoint of ASAS20, the key secondary endpoint of ASAS40 and a select set of secondary endpoints at Week 16 tested in the sequence below: ASAS20, ASAS40, change from baseline in ASDAS_{CRP}, change from baseline in hsCRP, change from baseline in ASQoL, change from baseline in SF-36v2 Physical Component Summary (PCS), change from baseline in BASMI, and change from baseline in the FACIT-F Total score. When an endpoint fails to declare statistical significance, this endpoint and the remaining endpoints lower in the hierarchy will be considered non-significant. The rationale for the selection and ordering of the select set of secondary endpoints are clinical importance, precedence and likelihood of statistical success based on the results of the A3921119 study.

Type I Error Control for Endpoints in the ASAS Family: Δ in Patient Global Assessment (PGA) of disease, change from baseline in total back pain, Δ BASFI, and change from baseline in inflammation (average of questions 5 and 6 of BASDAI) are the 4 ASAS components used in deriving ASAS20, thus they are considered belonging to the ASAS family of endpoints. A step-down testing procedure will be applied to them and tested in the sequence below: ASAS20, change from baseline in PGA, change from baseline in total back pain, change from baseline in BASFI, and change from baseline in inflammation (average of questions 5 and 6 of BASDAI) at Week 16. When an endpoint fails to declare statistical significance, this endpoint and the remaining endpoints lower in the hierarchy will be considered non-significant. Though this testing scheme does not protect the Type I error for the family of all possible comparisons, it will provide Type I error protection for testing the family of ASAS endpoints.

Type I Error Control for ASAS20 at Earlier Time Points: In order to be more rigorous about establishing the onset of efficacy as measured by ASAS20 at the earliest time point at which

there is statistical separation between tofacitinib 5 mg BID and placebo, a step-down approach with the ASAS20 from Week 16 to earlier time points (order of testing: Weeks 16, 12, 8, 4, and 2) will also be used for each time point. Though this testing scheme does not protect the Type I error for the family of all possible comparisons, it will provide Type I error protection for testing the family of ASAS20 time points.

Type I Error Control for ASAS40 at Earlier Time Points: In order to be more rigorous about establishing the onset of efficacy as measured by ASAS40 at the earliest time point at which there is statistical separation between tofacitinib 5 mg BID and placebo, a step-down approach with the ASAS40 from Week 16 to earlier time points (order of testing: Weeks 16, 12, 8, 4, and 2) will also be used for each time point. Though this testing scheme does not protect the Type I error for the family of all possible comparisons, it will provide Type I error protection for testing the family of ASAS40 time points.

9.3. Safety Analysis

All the safety data will be summarized descriptively through appropriate data tabulations, descriptive statistics, and graphical presentations:

- Incidence and severity of adverse events;
- Categorical summary of absolute vital signs and vital sign changes compared to baseline by subject;
- Serious infections, defined as any infection (viral, bacterial, and fungal) requiring hospitalization or parenteral antimicrobials, will be summarized;
- Any safety events that trigger withdrawal of a subject;
- Safety laboratory tests will be summarized according to Pfizer standards.

Special attention will be given to the following safety criteria: neutrophil counts, lymphocyte counts, serum creatinine levels, platelet counts, transaminase levels, bilirubin levels (and other measures of liver function), events of anemia.

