6.4.2. Discontinuation Criteria (from the Investigational Product)

The investigational product will be discontinued in the event of any of the following:

- Serious infections, defined as any infection (viral, bacterial, and fungal) requiring parenteral antimicrobial therapy or hospitalization for treatment, or meeting other criteria that require the infection to be classified as a serious adverse event;
- Two sequential absolute neutrophil counts $<1.0 \times 10^9/L$ ($<1000/mm^3$);
- Two sequential absolute lymphocyte counts <500 lymphocytes/ mm^3 ;
- Two sequential hemoglobin values <8.0 g/dL (80 g/L) or decreases of $>30\%$ from baseline value;

- Two sequential platelet counts $<75 \times 10^9/L$ ($<75,000/mm^3$);
- Two sequential AST or ALT elevations ≥ 3 times the upper limit of normal with at least one total bilirubin value ≥ 2 times the upper limit of normal;¹
- Two sequential AST or ALT elevations ≥ 3 times the upper limit of normal accompanied by signs or symptoms consistent with hepatic injury (eg, new onset elevated PT/INR);¹
- Two sequential AST or ALT elevations >5 times the upper limit of normal, regardless of total bilirubin or accompanying signs or symptoms;¹
- Two sequential increases in serum creatinine $>50\%$ AND an absolute increase in serum creatinine >0.5 mg/dL ($44 \mu\text{mol/L}$) over the average of screening and baseline values;
- Two sequential creatine kinase (CK) elevations >10 times the upper limit of normal, unless the causality is known not to be medically serious (eg, exercise or trauma induced);
- A confirmed positive urine pregnancy test in a woman of childbearing potential;
- Any opportunistic infections considered significant by the investigator or the Sponsor;
- Requirement of rescue medication for more than 10 consecutive days;
- Subjects interrupting investigational product for more than 5 consecutive days during the double-blind portion or 28 consecutive days during the open-label treatment period or subjects who are less than 80% compliant with the dosage regimen for any two consecutive visit periods;
- Other serious or severe adverse events, in the opinion of the investigator or sponsor. Whenever possible, the investigator should consult with a member of the study team before discontinuation of the subject from the investigational product;
- If VTE is confirmed, discontinue treatment with tofacitinib.

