8.2.3. Serious Adverse Events

A serious adverse event is any untoward medical occurrence at any dose that:

- Results in death;
- Is life-threatening (immediate risk of death);
- Requires inpatient hospitalization or prolongation of existing hospitalization;
- Results in persistent or significant disability/incapacity (substantial disruption of the ability to conduct normal life functions);
- Results in congenital anomaly/birth defect.

Or that is considered to be:

- An important medical event.

Medical and scientific judgment is exercised in determining whether an event is an important medical event. An important medical event may not be immediately life-threatening and/or result in death or hospitalization. However, if it is determined that the event may jeopardize the subject or may require intervention to prevent one of the other AE outcomes, the important medical event should be reported as serious.

Examples of such events are intensive treatment in an emergency room or at home for allergic bronchospasm; blood dyscrasias or convulsions that do not result in hospitalization; or development of drug dependency or drug abuse.

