8.2.4. Infections

Some infections may be classified as serious infections, as defined below.

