8.2.5. Serious Infections

A serious infection is any infection (viral, bacterial, and fungal) that requires hospitalization for treatment or requires parenteral antimicrobial therapy or meets other criteria that require it to be classified as a serious adverse event. A subject who experiences a serious infection should be discontinued from the investigational product and the serious adverse event should be listed as the reason for discontinuation in the CRF. Appropriate laboratory investigations, including but not limited to cultures should be performed to establish the etiology of any serious infection. All adverse events, including serious adverse events, should be reported as described in [Section 8](#) on Adverse Event Reporting.

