6.6. Safety Summaries and Analyses

All the safety data will be summarized descriptively through appropriate data tabulations, descriptive statistics, and graphical presentations. AEs, vital signs, 12-lead ECG parameters, and laboratory tests will be summarized according to the Clinical Data Interchange Standards Consortium (CDISC) and Pfizer Standards (CaPS).

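### Protocol 9.3 summarises serious infections on a narrower definition than the protocol's own definition in 8.2.5

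*Protocol*

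**What the plan says.** The protocol explains what a serious infection is in four places.

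- **Section 8.2.5 (Serious Infections)** says it is an infection that "requires hospitalization for treatment or requires parenteral antimicrobial therapy or meets other criteria that require it to be classified as a serious adverse event". Section 8.2.4 sends the reader there for the meaning: "Some infections may be classified as serious infections, as defined below".
- **Section 6.4.2 (Discontinuation Criteria)** lists parenteral antimicrobial therapy and hospitalization for treatment, then adds "or meeting other criteria that require the infection to be classified as a serious adverse event". The list opens with mandatory wording: "The investigational product will be discontinued in the event of any of the following".
- **Section 9.3 (Safety Analysis)** does not refer back to 8.2.5. It restates the term: "Serious infections, defined as any infection (viral, bacterial, and fungal) requiring hospitalization or parenteral antimicrobials, will be summarized".
- **Section 5.5 (Administration), open-label paragraph**, allows a temporary interruption of up to 28 days for infections that are not serious. Its parenthesis explains the term by parenteral therapy or hospitalization only.

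The SAP does not define serious infection. Section 6.6 says adverse events, vital signs, ECGs and laboratory tests "will be summarized according to the Clinical Data Interchange Standards Consortium (CDISC) and Pfizer Standards (CaPS"). Sections 3.5 and 6.6.1 say that adverse events of special interest (Tier 1) are summarised descriptively from a list kept in a separate safety surveillance plan.

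**The concern.** One term carries two definitions in the same protocol, and the analysis section has the narrower one. Section 1.2.3.2 names serious infection as a potential risk of tofacitinib. The Amendment 1 rationale (change log, item 36) says that serious infection events will be compared with other tofacitinib studies and with external databases. A count used in that way needs a single stated case definition. If the programmer follows 9.3 as written, the reported number could be smaller than the number of infections that investigators classified as serious under 8.2.5.

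A secondary point applies to the open-label period only. A site that reads the parenthesis in 5.5 on its own could hold drug for an infection for which 6.4.2 requires permanent discontinuation.

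**Working it through.** There is no sample size, power or event figure to reproduce. The check compares the definitions limb by limb and then asks whether the missing limb can matter.

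**Step 1. Compare the definitions.**

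| Protocol section | Purpose | Hospitalization | Parenteral antimicrobials | Other SAE criterion |
|---|---|---|---|---|
| 8.2.5 | Definition for AE reporting | Yes (for treatment) | Yes | Yes |
| 6.4.2 | Stopping investigational product | Yes (for treatment) | Yes | Yes |
| 9.3 | Safety summary | Yes | Yes | No |
| 5.5, open-label | Temporary interruption | Yes | Yes | No |

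Two of the four places have three limbs and two have two. Section 9.3 also leaves out the qualifier that hospitalization be for treatment, so on that limb it is slightly broader than 8.2.5. The definitions therefore differ in both directions.

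**Step 2. Can the third limb be met alone?** Yes. The seriousness criteria in 8.2.3 include death, a life-threatening event, persistent disability and an important medical event. Of the last, 8.2.3 says: "An important medical event may not be immediately life-threatening and/or result in death or hospitalization". In practice the main case is an infection treated orally as an outpatient and judged medically important. Under Section 8.1 the sponsor may also upgrade a non-serious event to serious, so the limb does not depend on the site alone.

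**Step 3. Follow such an infection through the plan.**

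- 8.2.5: it is a serious infection.
- 6.4.2: investigational product must be stopped.
- 9.3, read literally: it is not in the serious-infection summary.

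**Step 4. Does the SAP repair this?** Section 9 of the protocol permits it: "This analysis plan may modify what is outlined in the protocol". The SAP does not use that permission here. It neither repeats the two-limb wording nor restores the third limb, and the standards and list it relies on are not part of these documents. In the available text, 9.3 is the only definition given for the analysis.

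**Step 5. What stays visible?** The event is an SAE and is recorded on the CRF (8.1.4.2). It counts in adverse event incidence under 9.3. If it stops treatment, it also counts among the safety events that trigger withdrawal. The Amendment 1 rationale further plans tables by the MedDRA infections class.

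**The case against.** The strongest reply is that no undercount has been shown. Section 9.3 is an outline; the tables follow sponsor standards and a compound-level list that may already use three limbs. This stands, and it makes the consequence conditional. It does not remove the conflict in the text.

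A second reply is that a narrower analysis definition can be deliberate. Hospitalization and parenteral therapy are fairly objective, whereas an important medical event rests on judgment, and a fixed definition helps comparison across studies. That would be a reasonable choice, but nothing in the documents says it was made. If it was, the summary should be labelled as differing from 8.2.5.

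A third reply is that the event appears elsewhere and that safety is watched separately by the external data monitoring committee (9.5) and the opportunistic infection review committee (9.6). This is largely right. The withdrawal summary is an incomplete backstop: adverse events are collected for at least 28 days after the last dose (8.1.4), and an infection arising then triggers no withdrawal.

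On 5.5, the main clause already limits interruption to infections that are not serious, and the parenthesis can be read as a short gloss. Read together, 6.4.2 should govern. What remains is a risk of misreading at a site, not a conflict that cannot be resolved.

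**Conclusion.** The concern holds as a minor inconsistency. As written, 9.3 would leave out of its serious-infection summary some infections that the protocol itself classifies as serious. The wording mismatch is certain. The undercount is conditional: it requires that 9.3 be programmed literally and that at least one infection qualify through the third limb alone. The documents give no expected rate of serious infection and no share that would qualify only in that way, so the size cannot be stated and may be zero. No efficacy result, significance level, sample size or data collection is affected.

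**What to change.** - In Section 9.3 write: *Serious infections, as defined in Section 8.2.5, will be summarized.*
- In the open-label paragraph of Section 5.5 replace the parenthesis with *(see Section 8.2.5)*.
- Apply one matching derivation rule in the programming of the serious-infection table. If a two-limb count is wanted for comparison across studies, show it as a separately labelled row.

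The cost is two wording changes and one derivation rule, using data already collected. The only downside is that the reported count may be slightly higher.
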